4.4.2. Secondary outcomes

- 1. Olerud and Molander Ankle Score (OMAS): The OMAS is an established validated nine-item, patient-reported outcome measure developed and validated for use in clinical trials assessing symptoms following ankle fracture [35]. It contains nine items: pain, stiffness, swelling, stair climbing, running, jumping, squatting, supports and work/activities of daily living. Item responses are each scored from 0 to 25, with 0 representing the most severe state. The scale scores representing each dimension are produced by summing the responses to each item within that dimension. Raw scale scores are then converted to a metric (0-100; 0=most severe) [35]. The OMAS will be collected once at baseline (patients will be asked to complete it thinking about the week before ankle fracture) and then at 3, 6, 12 and 24 months follow-up.
- 2. *EuroQol 5 Dimensions (5L) Score (EQ5D-5L):* The EQ-5D-5L measures health-related quality of life in terms of 5 dimensions: mobility, ability to self-care, ability to undertake usual activities, pain and discomfort, anxiety and depression. Each dimension has five possible responses (no problems, slightly problems, moderate problems, severe problems and unable or extreme problems). The EQ-5D-5L will be scored according to the User Guide [36]. EQ-5D-5L data will be collected twice at baseline: *i.e.* once to assess patient health related quality of life on the day (after the injury) and once with regard to patient health related quality of life during the week before injury; then once each at 3, 6, 12 and 24 months. At baseline, the EQ-5D-5L will be collected before randomisation by patients who have capacity to consent at that time; or at the earliest opportunity after randomisation, by patients who consent having regained capacity.
- 3. *Complications:* Data on all further surgical procedures and other complications, e.g. deep wound infection (using Centres for Disease Control and Prevention definition), superficial infection, pin site infection (defined using the 'Good, Bad and Ugly' pin site grading system [37]), rehospitalisation, blood clots, wound dehiscence, septic arthritis, secondary interventions for non-union and all other secondary procedures will be

- collected by Research Nurses using CRFs for infections and hospital records at 3, 6, 12 and 24 months.

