4.7. Randomisation

Randomisation will be undertaken by York Trials Unit. When patients have consented and their baseline forms have been completed, the recruiting research associate/nurse/clinician will contact York Trials Unit (YTU), either by telephone or via the internet, to access a secure randomisation service. The randomisation service will record information and check patient eligibility to avoid inappropriate entry of patients into the trial. When a patient has a pilon fracture in both ankles, a specific ankle will be chosen prior to randomisation at the treating surgeon's discretion. YTU will then perform independent random allocation in a 1:1 ratio to internal fixation or external fixation, using computer generated random permuted blocks of random sizes, stratified by centre.

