5.4.3. Statistical analysis - main trial

A CONSORT flow diagram will be provided to display the flow of participants through the study (see Figure 2). The number of participants withdrawing from the trial will be summarised with reasons where available. Baseline characteristics will be presented by trial arm both for the trial population as randomised and for those patients for whom primary outcome data was available at 12 months follow-up. Statistical analyses will be on intention to treat (ITT) basis with patients being analysed in the groups to which they were randomised. Statistical significance will be at the 5% level, and analyses will be conducted in the latest available version of Stata or similar statistical software. All trial outcomes will be reported descriptively by trial arm at all time points at which they were collected. Continuous PROMS data will be summarised as means, standard deviations, medians and ranges, whereas data on further procedures and complications will be summarised as frequencies and percentages. Outcomes will be illustrated graphically over time where appropriate, including confidence intervals.

The primary analysis model will be a mixed effects regression analysis, with DRI scores at 3, 6 and 12 months follow-up as the dependent variable, adjusting for baseline DRI, randomised treatment arm and other pertinent baseline characteristics as fixed effects and including treating centre and surgeon as random effects. We will consider adjusting on fracture type and baseline DRI; however we will first monitor how well fracture type and baseline DRI are collected during the pilot phase to determine whether these adjustments are feasible. The model will account for similarities of scores by the same person by means of an appropriate covariance structure. The estimated treatment group differences at 12 months will be reported as the primary endpoint with 95% confidence interval and associated p-value. Secondary analyses of

the primary outcome will include an estimate of treatment group differences at 3 and 6 months from the same model. A separate model additionally including 24 month data will derive treatment group differences at that point. The overall treatment effect across all prior time points will be derived at 12 and 24 months (equivalent to area under the curve estimates).

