The amount of missing data will be mitigated by including 3, 6 and 12 month data in the primary analysis model, which allows the inclusion of any patient with complete baseline data and valid outcome data at one or more follow-up points. The nature of missingness for outcome data will be explored and multiple imputation and/or deviations from the missing-at-random assumption considered if appropriate.

There will be two exploratory subgroup analyses of the primary outcome, to assess the effectiveness of the different treatments across different patient subgroups. One will consider the impact of baseline patient preferences, whereby an interaction between treatment arm and patient preference (receipt of preferred treatment, non-preferred treatment, no prior preference) will be added to the primary analysis model. The other will consider fracture types (C1+C2 vs C3), whereby an interaction between treatment arm and fracture type will be added into the primary analysis model. These interactions will be presented graphically, and the p-value of the interaction will be reported. While there is insufficient statistical power for these interactions, they may help inform further research.

We will consider the impact that time to surgery has on the primary outcome by reporting DRI scores descriptively for the four patient groups formed by considering treatment allocation together with time to surgery (early (within 36 hours) Vs. late).

Secondary continuous PROMS outcomes will be analysed by similar mixed effects regression analyses to the primary analysis model. Binary secondary outcomes of additional procedures and complications will be analysed by mixed effects logistics regression analyses.

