Figure 2: ACTIVE Trial CONSORT flow diagram Inclusion criteria: Patients with closed Type C Exclusion criteria: Pilon fractures of the distal Prior failed fixation; Aged ≥16 years; tibia identified (AO 43 - C1, Pathologic fracture; With closed pilon fractures, C2 and C3) by member of classified AO 43- C which can be bi-Patient unable to understand lateral and patients with polytrauma; research team and recorded instructions for treatment on the screening log > 21 days since injury Where the treating surgeon believes the patient will benefit from surgical Pre-existing skin condition which precludes open surgery fixation. Not eligible Eligible Study set up & internal pilot Phase 1: 0-18 months Patient has capacity - obtain consent Patient lacks capacity (e.g. temporary cognitive impairment), approach consultee No consent Consultee declines Consent - Baseline Consultee agrees DRI, OMAS Randomise EQ-5D-5L Patient preferences Main recruitment, follow up to primary end point I year, main HTA report and Internal plate fixation (167 External fine wire fixation (167 patients) patients) Received allocated intervention (n=) Received allocated intervention (n=) Did not receive allocated intervention Did not receive allocated intervention (n & reasons) (n &reasons) Perioperative data collected Perioperative data collected Use of physiotherapy recorded Use of physiotherapy recorded Approach patient when regains capacity 3 months after randomisation Qualitative study: If consents: (12-month pilot phase) Outcome measures as at baseline, resource use and loss Collect EQ-5D-5L to follow-up Up to 30 patients who either If declines: Participant consent (n=15-20) or do not withdrawn as postconsent (n=5-10) to the 6 months after randomisation randomisation ineligible main trial. Outcome measures as at baseline, resource use and loss to follow-up 15-20 participating surgeons and trial recruiters 12 months after randomisation Outcome measures as at baseline, resource use and loss to follow-up Phase 2: 19-92 months 24 months (2/3rds sample) after randomisation Outcome measures as at baseline, resource use and loss Abbreviations to follow-up

Analysis

Draft HTA Report; dissemination

dissemination

index

DRI – Disability rating

OMAS - Olerud and

Molander Ankle Score EQ-5D-5L - EuroQoL 5 dimension 5 level

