7.2.2. Consultee consent – patients who lack capacity

A proportion of patients may be unconscious or may experience head injury and therefore lack capacity to make an informed decision about their participation in the research project; or are taking opiate-based pain killers which means their mental capacity may be impaired. In these instances we will consult with a Personal or Professional Consultee in line with the Mental Capacity Act 2005. Where a personal or professional consultee has agreed on behalf of a patient to take part, we will seek formal written consent retrospectively from the patient for continuation in the trial at the earliest appropriate time once they regain capacity. A patient information leaflet and consent form will be provided for review and the patient will have the opportunity to ask questions of the study team and to discuss the study with their friends or family before reaching a decision. They will then be asked to confirm their willingness to continue in the study and indicate this by signing the study consent form. If patients do not wish to enrol in the trial after a Personal or Professional consultee has been consulted, they will be withdrawn from the trial. We planned to implement this consultee process in Scotland according to their legal frameworks; that is, the Adults with Incapacity (Scotland) Act, 2000. However, Scotland A Research Ethics Committee advised that we could not recruit patients who lack capacity to consent as according to their legislation the research is not connected with the treatment of the adult's incapacity. Northern Ireland will also not recruit patients who lack capacity to consent as it will be a rare occurrence and it's most likely the patient will receive internal fixation because of the understanding that is required of a patient when being rehabilitated with a frame. Specific consent will be sought to facilitate the sharing of identifiable data with YTU as part of the study to facilitate the collection of outcome data.

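### The primary model is limited to patients with complete baseline data, but consultee-route patients have no stated way to supply a baseline DRI, so observed follow-up DRI scores could be discarded

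*Protocol*

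**What the plan says.** **Who enters the primary model.** Protocol section 5.4.3 describes a mixed model for DRI at 3, 6 and 12 months, "adjusting for baseline DRI, randomised treatment arm and other pertinent baseline characteristics as fixed effects". It says the repeated-measures approach "allows the inclusion of any patient with complete baseline data and valid outcome data at one or more follow-up points". The multiple imputation mentioned next is for missing outcomes.

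**Analysis principle.** The same section says: "Statistical analyses will be on intention to treat (ITT) basis with patients being analysed in the groups to which they were randomised".

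**Whether baseline DRI is a covariate.** The sentence after the model statement turns the adjustment into something to be considered: "we will first monitor how well fracture type and baseline DRI are collected during the pilot phase to determine whether these adjustments are feasible".

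**Timing of baseline forms.** Section 4.7 places randomisation at a point described as "When patients have consented and their baseline forms have been completed", with no exception for consultee enrolment.

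**Consultee route.** Section 7.2.2 admits patients who are unconscious, have a head injury, or "are taking opiate-based pain killers which means their mental capacity may be impaired". Those who later consent continue in follow-up.

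**Late baseline.** For the EQ-5D-5L, section 4.4.2 allows completion before randomisation "or at the earliest opportunity after randomisation, by patients who consent having regained capacity". In Figure 2 the instruction at the point where such a patient consents is "Collect EQ-5D-5L". Section 4.4.1 and Table 1 list a baseline DRI for participants generally. They do not say when a patient without capacity would complete it.

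**The concern.** A patient enrolled through a consultee, who regains capacity and returns the DRI at 3, 6 and 12 months, has supplied the primary outcome in full. Read as written, the complete-baseline condition leaves that patient out of the primary model for want of a covariate. That is complete-case deletion on a baseline variable. It throws away observed primary outcomes and moves the analysed set away from the randomised set.

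Section 7.2 says it would not be ethically sound to exclude patients lacking capacity, so the trial enrols this group on purpose and may then leave it out of its main result. The 20% allowance in section 4.5 is for attrition at one year. It does not mention responders who lack a baseline, and the revised 80% target has no margin to absorb them.

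**Working it through.** **Step 1. Do the trial's own procedures produce such patients?**

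- Consultee-route patients are randomised while lacking capacity (section 7.2.2), so they cannot complete a patient-reported form first, as section 4.7 assumes.
- If they regain capacity and consent, they stay in follow-up. If they still lack capacity at 3 months, they are withdrawn (section 7.2.3).
- A late-baseline rule is written for the EQ-5D-5L and for no other instrument.
- The outcome-missingness provision does not reach a missing baseline value.

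So randomised patients with follow-up DRI and no pre-randomisation baseline DRI are foreseeable. They are lost if baseline DRI is a covariate and the complete-baseline condition is applied.

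**Step 2. Reproduce the planned sample size** (section 4.5: difference 8, SD 20, 5% significance, taken as two-sided).

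Normal approximation, n per arm = 2(z₁ + z₂)² × SD² / difference²:

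- 80% power: 2 × (1.960 + 0.842)² × 400/64 = 98.1, so 99. The t-test version gives 99.1, so 100, as stated. 100/0.80 = 125 per arm, 250 in total.
- 90% power: 2 × (1.960 + 1.282)² × 400/64 = 131.3, so 132. The t-test version gives 132.3, so 133, as stated. 133/0.80 = 166.25, so 167 per arm, 334 in total.

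Both stated targets reproduce; no figure in section 4.5 is wrong.

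**Step 3. Power when responders without a baseline are excluded.** The protocol does not give the share, so it is an assumption, varied from 0 to 20%. Two-sample t, with noncentrality 0.4 × √(n/2) and 2n − 2 degrees of freedom, starting from 100 responders per arm at the 250 target:

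| Share excluded | Patients lost | n per arm | Noncentrality | Power |
|---|---|---|---|---|
| 0% | 0 | 100 | 2.828 | 80.4% |
| 2% | 4 | 98 | 2.800 | 79.6% |
| 5% | 10 | 95 | 2.757 | 78.3% |
| 10% | 20 | 90 | 2.683 | 76.1% |
| 20% | 40 | 80 | 2.530 | 71.0% |

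At the 334 target the same calculation gives 90.3% with no exclusion, 88.8% at 5%, 87.1% at 10% and 82.9% at 20%.

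**Step 4. Direction.** Consent route is determined before allocation, so exclusion by route should fall about equally on the two arms. The arithmetic therefore measures lost precision and says nothing about bias.

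**The case against.** **The adjustment is conditional.** Section 5.4.3 foresees incomplete baseline DRI and makes the adjustment depend on the pilot. Without that covariate, these patients need not be lost. This stands, and the point is conditional for that reason. But the preceding sentence states the adjustment outright, and the complete-baseline condition and the other baseline characteristics remain either way. Dropping baseline DRI for everyone is also a blunt answer to a gap in a few patients.

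**This is SAP detail.** The sentence on complete baseline data explains how the model reduces missing outcomes and is not a formal analysis-set definition. How to fill a covariate could properly be left to the SAP. The objection here is to the condition the protocol states, not to the missing detail.

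**Stronger readings a reader might infer.**

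- *Consultee-route patients give the EQ-5D-5L and nothing else.* No sentence says so. Section 4.4.1 and Table 1 exempt nobody from baseline DRI, and the Figure 2 text is jumbled by extraction. The documents support only silence on late DRI collection.
- *The comparison is biased or the intention-to-treat statement broken.* Nobody changes group, which is how the protocol defines the principle, and the loss should be roughly balanced.
- *The most severely injured are removed.* Lack of capacity is not fracture severity or polytrauma, and opiate use is described only as something that may impair capacity.
- *The loss is large.* The share is unknown. Scotland and Northern Ireland do not recruit patients lacking capacity, section 7.2.2 expects them to be rare in Northern Ireland, and section 4.5 lets recruitment run past 250.

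**Conclusion.** The point holds in a limited form. If baseline DRI is kept as a covariate, the stated entry condition would discard observed primary outcomes from randomised patients whom the trial deliberately enrols, and nothing in the protocol recovers them. The harm is lost precision and a less representative analysed set; bias between arms is not shown.

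At the 250 target, the first 5% of responders excluded costs about 2 points of power, and 10% costs about 4 (80.4% to 76.1%). These figures rest on an assumed share and on a simple two-sample t calculation at 12 months, which ignores any gain from repeated measures or covariate adjustment. They are a guide to scale, not a forecast.

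This is a cheap improvement well worth making. It does not put the trial's validity in doubt.

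**What to change.** 1. In section 5.4.3, replace the complete-baseline condition with a statement that every randomised patient with at least one DRI at 3, 6 or 12 months enters the primary model.
2. State that a missing baseline covariate is filled with its mean over both arms, ignoring allocation. Alternatively, model baseline DRI jointly with the follow-up scores.
3. Reconcile the two sentences on baseline DRI so that it is clear whether it is a covariate.
4. Say whether a pre-injury DRI is collected when capacity returns. Section 4.7.1 says patients are told their allocation, so a recalled score taken after randomisation could be influenced by it. It should not be the covariate in the primary model; at most it is descriptive or for a sensitivity analysis.

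Items 1 to 3 need only wording, settled before the analysis. The downside is slightly less precise adjustment for patients whose baseline is filled in. Item 4 costs one questionnaire, if it is added, at a contact that already takes place.

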- 3.1. Non-union, mal-union and secondary arthritis. Non-union will be defined as inability to heal as confirmed on x rays / CT scan or as secondary intervention for failure to heal. Mal-union is defined by a standard measurement based on Dror Paley's technique, undertaken using final radiographs at 12 months. Secondary arthritis in the ankle will be assessed using the Kellgren and Laurence scale [38].
- 3.2. To undertake these assessments we will use routine standard radiographs (anterior-posterior and lateral tibia views, with a focus on the ankle for the latter view) and/or when necessary a CT scan of the tibia, fibula and/or ankle, which will be taken at 12 months after the injury. Assessment of imaging will be undertaken by the treating surgeon at the participating site using a proforma which will then be returned to the coordinating centre.
- 4. **Resource use and work impact:** Data on resource use and work impact will be collected to inform the economic evaluation (e.g. length of hospital stay, rehospitalisation and return to work). This data will be gathered through a brief questionnaire administered to patients at 3, 6, 12 and 24 months and hospital records. Table 1 outlines the schedule of events.
- 5. **Patient preference for treatment:** Data on patient preferences will be collected as part of the patient-completed questionnaire to inform the primary statistical analysis model. Patients will be asked about their preferred treatment; and to state if they have no treatment preference at the baseline and 12 month follow-up questionnaire. At 12 month follow-up patients would be asked to state their preference by imagining if they had the same injury again.
- 6. *Transition question:* To assist interpretation of findings, patients will be asked at the 12-month follow-up time-point whether compared with when they initially sustained the pilon fracture one year previously, how their ankle is currently. This will help us to describe clinically important changes for patients, should we identify a difference between the two treatment groups.
- 7. *Free text comments:* Patients will be given the opportunity to highlight any additional issues relevant to their ankle and its impact on their daily activities at the 3, 6, 12 and 24 month time-points.

In Table I we outline the schedule of events for ACTIVE.

Table 1: ACTIVE Schedule of events

Time-point	Baseline	3 month follow- up	6 month follow-up	12 month follow-up	24 month follow- up
PROMS					

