4.7.1. Allocation concealment and blinding

Patients and treating clinicians will be informed of the allocation. Web- or telephone-based randomisation will ensure concealment of the allocation sequence. However, as with many surgical trials, where the surgical site is clearly visible, it is not feasible to blind patients, surgeons or outcome assessors to their allocation. The primary outcome is a patient-reported measure. Outcome bias will also be mitigated somewhat by both groups of patients receiving routinely available surgical treatments. We will also collect data on patient and surgeon preferences; for patients we will also ask those who do not consent for their preferences for treatment. We will account for whether patients received their preferred treatment in a secondary analysis. Staff analysing questionnaire responses will be blind to patients' treatment allocation. All recruiting centres will have surgeons who are familiar with the two techniques and perform them as part of routine NHS care.

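### The preference subgroup crosses arm with a variable that already depends on arm, so the reported interaction p-value does not test whether the direction of preference changes the treatment effect

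*Protocol*

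**What the plan says.** Protocol section 5.4.3 introduces the subgroup work as follows: "There will be two exploratory subgroup analyses of the primary outcome, to assess the effectiveness of the different treatments across different patient subgroups". Of the preference analysis it says "One will consider the impact of baseline patient preferences", and it then fixes the model term: "an interaction between treatment arm and patient preference (receipt of preferred treatment, non-preferred treatment, no prior preference". On reporting it says "These interactions will be presented graphically, and the p-value of the interaction will be reported". It adds the caveat "While there is insufficient statistical power for these interactions, they may help inform further research".

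Section 4.4.2 describes what is collected: "Patients will be asked about their preferred treatment; and to state if they have no treatment preference at the baseline and 12 month follow-up questionnaire". The direction of preference is therefore recorded at baseline.

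The SAP was not available. The protocol itself nevertheless names the variable, its three levels, the model term and the p-value to be reported.

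**The concern.** The aim is a baseline subgroup, but the stated variable is not one. Whether a patient with a preference falls in the preferred or the non-preferred level depends jointly on the baseline answer and on the allocation. The preferred level sets internal-preferers given internal fixation against external-preferers given a frame; the non-preferred level does the reverse. Within either level the arm comparison is between different kinds of patients and is not randomised.

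If patients who want a frame have a different outlook from those who want a plate, for reasons unrelated to treatment, that difference enters the interaction and can be read as preference modifying the treatment effect. If receiving the unwanted treatment does harm recovery, the reported p-value does not respond to it. The fracture-type subgroup in the same section uses a baseline variable and does not have this problem.

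**Working it through.** **Inputs.** From Protocol section 4.5: difference of 8 DRI points, SD 20, 5% level (taken as two-sided), 100 per group at 80% power, 20% attrition. These reproduce. The normal approximation gives 2(1.960 + 0.842)² × 20²/8² = 98.1, rounded up to 99; the t-test version gives 99.08, rounded up to 100. Then 250 × 0.8 = 200 analysed, and 334 × 0.8 = 267 under the larger target. The protocol gives no preference shares, no prognostic gap and no power for this subgroup, so everything below that uses them is an assumption.

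**Algebra.** Let m_int, m_ext and m_none be the mean outcome in each baseline preference group, averaged over arms. Let τ_int, τ_ext and τ_none be the internal-minus-external effect in each. The arm difference within each planned level is:

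- Preferred: (m_int + τ_int/2) − (m_ext − τ_ext/2) = (m_int − m_ext) + (τ_int + τ_ext)/2
- Non-preferred: (m_ext + τ_ext/2) − (m_int − τ_int/2) = −(m_int − m_ext) + (τ_int + τ_ext)/2
- No preference: τ_none

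The two interaction degrees of freedom are therefore:

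1. Preferred minus non-preferred = 2(m_int − m_ext). This is prognosis only.
2. Average of those two levels minus no preference = (τ_int + τ_ext)/2 − τ_none. This is a genuine comparison of arm effects.

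τ_int − τ_ext appears in neither. It sits in the main effect of match: preferred minus non-preferred, averaged over arms, equals (τ_int − τ_ext)/2. The plan does not commit to reporting a p-value for that term.

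**Size when preference does not modify the effect.** Take 200 analysed, 1:1 allocation, 30% preferring each treatment and 40% neither, so 30 patients in each of the four preference cells. With prognostic gap Δ, the first contrast is 2Δ with variance 20² × 4/30 = 53.3, and the noncentrality is (2Δ)²/53.3. The 2-df F test (2 and 194 df) then gives:

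| Gap Δ (points) | Noncentrality | Planned test rejects | Direction coding rejects |
|---|---|---|---|
| 2 | 0.30 | 7% | 5% |
| 4 | 1.20 | 15% | 5% |
| 5 | 1.88 | 21% | 5% |
| 8 | 4.80 | 48% | 5% |
| 12 | 10.80 | 84% | 5% |

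Other shares at an 8-point gap with 200 analysed (prefers one / prefers other / none):

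| Shares | Planned test rejects |
|---|---|
| 15/15/70 | 26% |
| 40/10/50 | 28% |
| 25/5/70 | 16% |
| one third each | 53% |

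With 267 analysed and one third each it is 66%. Direction coding stays at 5% throughout.

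**Size when preference does modify the effect.** Suppose the non-preferred treatment costs c points, so τ_int = −c, τ_ext = +c and τ_none = 0, with no prognostic gap. Both planned contrasts are then zero and the planned test stays at 5%. Under the 30/30/40 split, direction coding has 15% power at c = 4 and 48% at c = 8. Those costs are differences of 8 and 16 points between the two groups' arm effects.

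**The legitimate degree of freedom.** For an 8-point difference in arm effect between patients with any preference and those with none, the noncentrality is 8²/(20²/30 + 20² × 2/40) = 64/33.3 = 1.92. Power is about 22% under either coding.

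These figures treat the 12-month score as one independent measurement per patient without covariates, which is simpler than the planned mixed model.

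**The case against.** The best defence is that little rides on this analysis. The protocol labels it exploratory and admits low power. Section 5.4.1 says exploratory subgroups will be pre-specified in a SAP, which may already set this right. That lowers the severity. It does not rescue the stated term: low power is a different weakness, and the planned test does not gain power for the contrast of interest at any sample size.

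A second defence is that the six arm-by-preference cells are the same under both codings, and the interaction is to be graphed. This is right. A reader might infer that a real preference effect would be lost. The protocol does not support that, because the effect could be seen in the graph and in the main effect of match. What is wrong is the term to which the reported p-value belongs. A reader might also infer that this p-value is nothing but prognosis; the second degree of freedom shows otherwise.

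Third, the bracketed levels might only describe the groups that result from crossing arm with direction of preference. The introductory mention of baseline preferences gives this some support, but the literal wording makes match the factor that interacts with arm.

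Fourth, adjustment for baseline DRI and other characteristics may narrow the prognostic gap. It cannot bring τ_int − τ_ext into the interaction.

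Finally, section 4.7.1 says "We will account for whether patients received their preferred treatment in a secondary analysis". A reader might take this as a second instance of the error. It specifies no interaction with arm, and a main effect of match would carry the right contrast, so it is not one.

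**Conclusion.** The point holds as a mis-specified exploratory analysis. The algebra depends on no assumption about shares or gaps: one interaction degree of freedom is prognosis, one is a valid comparison of any preference with none, and the comparison of internal-preferers with external-preferers is absent.

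The size does depend on assumptions that the protocol does not supply. With no effect modification, spurious rejection runs from barely above nominal (7% at a 2-point gap) to 48% at a gap as large as the trial's minimum important difference, and is 16% to 28% at that same gap when preferences are fewer or unbalanced. Conversely, true modification by direction of preference leaves the planned test at 5%, although the correctly coded test would itself have only modest power.

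A reader might infer that the trial's main conclusion is at risk. It is not: the primary 12-month comparison and the sample size do not use this variable, and the data needed for the right analysis are collected at baseline. This should be fixed before analysis; it is not a critical fault.

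**What to change.** In Protocol section 5.4.3, and in the SAP if it repeats the term, define the subgroup by the pre-randomisation answer alone: prefers internal, prefers external, no preference. Add its main effect and its interaction with randomised arm to the primary model. Report the 2-df interaction p-value and show the randomised arm difference at 12 months, with its confidence interval, within each of the three levels.

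If an effect of receiving the preferred treatment is wanted, report the internal-preferers versus external-preferers contrast of the arm effect from that same model, with match defined by allocated treatment so that it stays within intention to treat.

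The cost is a sentence or two of text. No new data are needed, and the primary model and the sample size stay as they are.
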